# **Informed Consent and HIPPA**

#### **Informed Consent Process**

Prior to performing any study related activities, potential participants will provide written informed consent. A qualified professional on the research team will inform each potential participant of the purpose of the project, possible risks, their personal rights, and potential benefits of the study. All possible exclusion criteria will be verified following informed consent, prior to screening. The informed consent form clearly states the rights of a participant, including the telephone number and email address for the Committee on the Rights of Human Subjects of the UNC School of Medicine. This office may be contacted in the event of perceived violation of rights. The informed consent forms are written in large print at a level understandable to the participants. For low-literacy participants, the consent form will be read aloud verbatim. The interviewers are highly experienced and have successfully completed ethics training. Participants will only be included if they have the capacity to give legally effective consent. We will not include participants who lack decision making capacity, so consent from legally authorized representatives will not be required. The original signed consent forms will be kept in a separate folder from the individual study folder. This folder will be stored in a locked file cabinet of the Applied Physiology Laboratory. Participants will be provided with a copy of the consent form for personal reference.

#### **Informed Consent Form**

See Appendix A.1 for Approved Consent form

#### **HIPPA Authorization**

See Appendix A.2 for HIPAA Authorization Form

The privacy and confidentiality of research participants are to be respected and protected at all times. This research study will comply with the HIPAA Privacy Rule as well as all other state, federal, and institutional regulations intended to protect the rights, safety, and welfare of human participants involved in research studies. We will attempt to minimize the collection, storage, and transmission of information containing participants' personal identifiers, and, whenever identifiers are necessary, protect against unauthorized access or disclosure. In addition, we will employ several rigorous procedures for protecting against risks to participant privacy and confidentiality of data. We will only collect and store information about study participants that is relevant to the research as outlined in the protocol. We will minimize the use of paper documents by entering the majority of study data directly into secure computer databases. All study databases will be password protected and only study team members whose job functions require access to these data will have permissions. Whenever possible, data will not be stored on laptop computers. Individual participant data will not be shared with individuals outside the study team, except as required by law and/or for regulatory purposes.

All study staff must regularly fulfill certification requirements in Human Subjects Protection training. Study personnel are also regularly trained in stringent computer and information security procedures. All electronic study data will be stored electronically on secure UNC servers, accessible only to study personnel.

Research study records will be maintained for no less than 7 years following the completion of the study, after which time personal identifying information will be removed. Research information in a participant's medical record will be kept indefinitely.

# Participant Evaluations and Follow-up

### **Timeline and Visit Schedule**

The current study consists of 27 total visits: 3 testing visits and 24 training sessions. All visits will take place at the Applied Physiology Laboratory and/or the Student Recreation Center. The three testing visits will consist of assessments of physical function, cardiorespiratory fitness, body composition, balance, symptoms, and muscular strength. These visits will occur at baseline, 6-weeks, and 12 weeks. The HIIT intervention will occur over the course of 24 separate training sessions, occurring two times per week for two 6-week sessions.

Week	Visit	Testing	Training	Measures Collected
	#			
0	1	X		
 
Physical function: 40 m fast-paced walk test, 30-s chairstand test, a stair-climb test, and Timed Up and Go Test
 
Knee OA Symptomatic Burden: WOMAC
 
Balance: single leg stance and side-by-side, semi-tandem, and tandem tests
 
Muscle Strength. isokinetic dynamometer for power at 60 degrees per second and for strength at 60 degrees of knee flexion.
 
Cardiorespiratory fitness: peak oxygen consumption (VO2peak)
 

				Body composition: DXA for fat mass, lean body mass, and visceral fat
1-5	2-11		X	
 
Heart rate: chest strap heart rate monitors to identify heart rate and intensity during each training bout
 
Ratings of perceived exertion: Borg perceived exertion scale
 
Severity of pain: visual analog scale of 0-10 (no pain-extreme pain) during and after exercise
 
Training bouts completed
 
Mode of exercise
 
Exercise enjoyment
 

6	12	X		
 
Physical function: 40 m fast-paced walk test, 30-s chairstand test, a stair-climb test, and Timed Up and Go Test
 
Knee OA Symptomatic Burden: WOMAC
 
Balance: single leg stance and side-by-side, semi-tandem, and tandem tests
 
Muscle Strength. isokinetic dynamometer for power at 60 degrees per second and for strength at 60 degrees of knee flexion.
 
Cardiorespiratory fitness: peak oxygen consumption (VO2peak)
 
Body composition: DXA for fat mass, lean body mass, and visceral fat
 

7-12	13-26		X	
 
Heart rate: chest strap heart rate monitors to identify heart rate and intensity during each training bout
 
Ratings of perceived exertion: Borg perceived exertion scale
 
Severity of pain: visual analog scale of 0-10 (no pain-extreme pain) during and after exercise
 
Training bouts completed
 
Mode of exercise
 
Exercise enjoyment
 

13	27	X		
 
Physical function
 
Knee OA Symptomatic Burden
 
Balance
 
Muscle Strength
 
Cardiorespiratory fitness
 
Body composition
 
Structured interview: barriers and concerns experienced with current training protocol; preference of exercise mode and instruction; opinions on what information participants would find helpful to transition to an at-home and or independent program
 

# **Concomitant Medications**

Use and changes of medications for OA will be monitored and recorded during the study but will not be a reason for exclusion. Subjects will be asked to self-report all medications that they are currently using and/or being prescribed during the 7 days prior to study enrollment at the baseline visit. At subsequent study visits, participants will be asked

to report any changes with their medications (e.g., discontinuation, new medications). Medications will be considered when conducting analyses and interpreting results.

# **Statistical Considerations**

## Aim 1 Analyses

Analyses will be primarily descriptive and will include data from all participants during their experience using HIIT. First, the flow of participants through the study (i.e., screened, recruitment, enrollment [along with refusals and ineligibility, with reasons], and follow-up at each time point) will be descriptively summarized using frequencies and proportions. Then, compliance and tolerability of HIIT (i.e., proportion of sessions completed, change in mode, number of training days per week, recovery days between sessions), along with 95% confidence intervals, will be summarized. We will also descriptively summarize pain on a 0-10 scale, during and after exercise, as well as participant enjoyment of exercise by training day, and will use informative graphical approaches where useful.

# Aim 2 Analyses

All available data from all enrolled participants, regardless of extent of adherence to HIIT, will be descriptively summarized in tables and graphs. Longitudinal models will be fit for all outcomes (physical function, knee OA symptomatic burden, balance, muscle strength, cardiorespiratory fitness, and body composition) using all available data with linear mixed models. Mixed models allow for inclusion of all observed outcome data for each participant under the assumption that any missing data are missing at random. No missing data will be imputed. Separate models will be fit for each outcome with no adjustments for multiple comparisons since this is an exploratory proof-of-concept study; however, data from all outcomes assessed will be reported regardless of "significance". For each model, fixed effects will include visit, gender, baseline BMI, age, and severity of baseline OA symptoms. Additionally, if at least 10% of participants are not using prescribed pain medications at each time point, we will include dichotomous use of pain medication as a time-dependent fixed effect. Each model will also include random participant effects to account for correlation between repeated outcome measurements. For each outcome, we will use the model to estimate the mean change from baseline to each follow-up visit along with 95% confidence intervals.

## Power and Sample Size.

For this study, we chose the 40 m fast-paced walk test as our primary measure of physical function on which to base power calculations based on recent recommendations. We assume that the standard deviation for walk times is 10 seconds, based on results from a study among patients with knee OA; in this study, the estimated standard deviation was 9.2 seconds, and we computed an upper 80% confidence bound of 10 seconds. We further assume that loss at 12 weeks would be at most 10%, and that correlation between repeated outcomes from the same participant would be at least 0.6 (a conservative value). Under these assumptions, enrolling 30 participants would provide at least 80% power to detect a mean 5-second difference between baseline and the 12-week assessment using a two-sided test at the 5% level.

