Three participants per month are expected to be enrolled with at least 80% retention during the study period. As part of Aim 1, adherence to and tolerability of HIIT, acceptability, and recruitment and retention rates of patients through 6- and 12-week assessments will be determined. This will be determined as the percent of participants that screen into the study versus those approached and the percent of participants retained at the 6- and 12-week post-tests. Frequency and reasons for initial refusal, ineligibility, and drop out will be collected. Adherence and tolerability will be evaluated based on number of sessions attended/completed, modifications, such as change in mode; number of training days per week; recovery days needed between sessions to complete training, and severity of pain on a scale of 0-10 (no pain-extreme pain) during and after exercise as a measure of tolerability. If the HIIT intervention is shown to be well-tolerated and promising, results of this preliminary study will lay the foundation for a large randomized controlled trial to establish the efficacy of HIIT as a revolutionary approach for enhancing the rehabilitation and management of knee OA.

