# Participant Screening and Eligibility Criteria

# **Participant Screening**

Individuals interested in the study will be screened for eligibility criteria via telephone, reducing the chance of participants coming to the lab for lab screening if they would be excluded based upon demographic factors or level of physical function, which have been outlined in the exclusion criteria. Individuals who meet eligibility criteria and are interested in participating will meet a study team member to complete informed consent and inclusion criteria. All potential patients will undergo a 12-lead electrocardiogram and will be cleared to participate following medical history review from Drs. [name] and [name]. Following clearance, baseline testing will occur.

Thirty patients with symptomatic knee OA will be recruited, which we will define as a diagnosis of knee OA and current knee symptoms in at least one knee. Patients with physician diagnoses of knee OA will be identified from University of North Carolina (UNC) electronic medical records. For current joint symptoms, participants must have a minimum score of 6 out of 20 on the Western Ontario and McMasters Universities Osteoarthritis Index (WOMAC), pain subscale. We will include participants 40-75 years old with body mass index of 18.5-50 kg/m2 because: 1) knee OA onset typically begins after age 40 and is more common with greater obesity, and 2) HIIT is well-tolerated in middle-aged to older adults who are normal weight, overweight, obese,

and morbidly obese. Inclusion of these participants will improve generalizability of study results to real-world patients.

We will aim to ensure that participant selection is equitable and all relevant demographic groups have access to study participation by contacting (via initial letter and telephone call) all participants who meet inclusion / exclusion criteria, regardless of demographic characteristics. We have also aimed to produce recruitment and intervention materials that are appropriate for individuals with low literacy or education levels. We will continue to recruit participants until we reach our sample size goal of N=30.

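### Does the stated 80% power fail because the protocol's retention expectation allows twice the loss assumed in the power calculation?

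*Combined protocol and SAP*

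**What the plan says.** Power and Sample Size takes an SD of 10 s for 40 m walk time. This is an upper 80% confidence bound around a source estimate of 9.2 s. It assumes that "correlation between repeated outcomes from the same participant would be at least 0.6 (a conservative value"), and on dropout it says "We further assume that loss at 12 weeks would be at most 10" per cent. With a two-sided 5% test it concludes that "enrolling 30 participants would provide at least 80% power to detect a mean 5-second difference between baseline and the 12-week assessment".

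The retention plan (Retention: Role of All Study Personnel) gives a different figure: "Three participants per month are expected to be enrolled with at least 80% retention during the study period".

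Participant Screening fixes the enrolment target: "We will continue to recruit participants until we reach our sample size goal of N=30". Nothing in the protocol provides for replacing dropouts.

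Under Aim 2 Analyses, each outcome is modelled "using all available data with linear mixed models", with random participant effects. Results are mean changes from baseline with 95% confidence intervals. There is no multiplicity adjustment, because the study is described as exploratory, and every outcome is to be reported whatever its significance.

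**The concern.** The power claim rests on at least 27 of 30 participants at week 12. The retention expectation is satisfied by 24. The study could therefore do what it expects on retention and still fall outside the conditions of its power statement, and the text does not say what power would then apply.

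Retention is itself an Aim 1 outcome, so the figure is not incidental. There is also little slack at 10% loss. By paired t-test, 27 completers give 79.8%, and 28 are needed to pass 80%. If 20% loss brought a real drop in power, the claim would be too favourable for a case the protocol contemplates, and a team planning the larger trial might rely on it.

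**Working it through.** **Inputs.** From Power and Sample Size: change 5 s, SD 10 s (source estimate 9.2 s), correlation 0.6, two-sided 5%, N = 30. Loss is 10% (27 completers) from that section, or 20% (24 completers) from the retention plan.

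**Step 1: reproduce the stated figure with a paired t-test.**
- SD of change = 10 × √(2 × (1 − 0.6)) = 8.944 s.
- Noncentrality = (5 / 8.944) × √n, with n − 1 degrees of freedom.
- n = 27: noncentrality 2.905, power 79.8%.
- n = 24: noncentrality 2.739, power 74.6%.

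The 27-completer result matches the stated 80% to within rounding.

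**Step 2: repeat with the planned analysis.** The plan does not discard people who miss week 12. A mixed model with random participant effects keeps their baseline, and their week 6 value if they have one. I took the generalised least squares variance of the baseline-to-week-12 contrast over three visits, with equal correlation of 0.6. The degrees of freedom are within-participant residual: observations − participants − 2. For example, 24 × 3 + 6 × 1 = 78 observations gives 78 − 30 − 2 = 46. The model's fixed covariates vary between participants and are left out, as they bear little on a within-participant contrast.

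| Completers | Dropouts leave | SE (s) | df | Power, t | Power, normal |
|---|---|---|---|---|---|
| 27 | before week 6 | 1.704 | 52 | 82.1% | 83.5% |
| 27 | after week 6 | 1.694 | 55 | 82.6% | 83.9% |
| 24 | before week 6 | 1.789 | 46 | 78.1% | 79.8% |
| 24 | half before, half after | 1.777 | 49 | 78.8% | 80.3% |
| 24 | after week 6 | 1.768 | 52 | 79.3% | 80.7% |

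With the harsher choice of completers − 1 degrees of freedom (23), the 24-completer figures are 76.3–77.3%. A simulation of 1,500 trials per pattern, fitting a random-intercept model by restricted maximum likelihood, gave 77.1–80.3% at 20% loss across both choices of degrees of freedom. Its Monte Carlo error is about 1 point.

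**Step 3: allow for the cautious inputs.** At 24 completers:
- SD 9.2 s, correlation 0.6: 81.3% by paired t-test; 84.5–85.5% with the mixed model on residual df.
- SD 10 s, correlation 0.65: 80.1% by paired t-test; 83.1–84.2% with the mixed model on residual df.

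**Step 4: effect on what is reported.** The half-width of a paired 95% interval is t × 8.944 / √n.
- n = 27: 2.056 × 1.721 = 3.54 s.
- n = 24: 2.069 × 1.826 = 3.78 s.

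The interval widens by 0.24 s on each side.

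**The case for a change.** The best case for a change is that a formal power claim should be tested at its own planning values, SD 10 s and correlation 0.6, and not rescued by better ones. At those values and 24 completers, the mixed model stays below 80% with any t reference, and only the normal approximation reaches it. If true retention were 80%, fewer than 27 of 30 would complete with probability 88%; at 85% retention the probability is 68%. Since the results are meant to inform a larger trial, one extra sentence would be cheap.

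Most of the arithmetic stands. The two loss figures do differ, no passage connects them, and power at 20% loss is slightly lower.

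The step from there to a defect does not stand. The power statement is explicitly conditional and true on its conditions. The binomial figures treat 80% or 85% as the true rate, whereas the protocol gives 80% as a floor. It also has the investigators review retention monthly and respond to problems (Identifying Potential Problems). The larger trial is tied to HIIT proving well tolerated and promising, not to one significance test, and its planners would work from the observed change, SD and retention. An added sentence would describe power more fully without altering any estimate, interval or decision. Raising the retention expectation to 90% so that the numbers match would change neither actual retention nor power.

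**Conclusion.** No change is called for. The two sections use different, compatible bounds, and the stated power is correct under its stated assumptions. If loss reached 20%, the planned mixed model would have about 78–81% power for a 5 s change (78.1–79.3% with residual degrees of freedom, 79.8–80.7% by normal approximation), so the gap from 80% is about 0 to 2 points.

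This rests on SD 10 s, equal correlation of 0.6 across the three visits, and dropouts contributing at least a baseline. With completers − 1 degrees of freedom the gap is nearer 3 to 4 points. Either an SD at the source value of 9.2 s or a correlation of 0.65 removes it under every reference used here.

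In an exploratory single-arm study that reports mean changes with intervals, this is an acceptable gap in description. An analyst can state power at the observed retention if anyone needs it. The sample size, analysis and conduct are unaffected.

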# **Analyses of Safety Data and OA Medications**

Any accumulated data on adverse events, particularly those adjudicated to be at least potentially related to HIIT, will be descriptively reported using frequencies and proportions. Additionally, medications prescribed for the treatment of OA will be descriptively summarized, along with changes in these medications over the course of the study. No inferential statistics will be presented for safety or medication data.

# **Safety Reporting Overview**

### Definitions

Adverse events will be determined using the NC TraCS Safety Monitoring Plan guidelines for Minimal Risk Studies. The Grading Scale is as follows:

- Mild Event results in mild or transient discomfort, not requiring intervention or treatment; does not interfere with daily activities (e.g. transient muscle soreness)
- Moderate Event is sufficiently discomforting so as to limit or interfere with daily activities; may require additional interventional treatment (e.g. musculoskeletal injury such as a muscle strain)
- Severe Event results in significant symptoms that prevent normal daily activities; may require invasive intervention

In the event that two adverse events are classified as either moderate or severe the study will be placed on hold in order to reassess the study procedures in order to decrease the risk of another adverse event. Based on previous data, the potential for adverse events are minimal. The potential benefits outweigh potential musculoskeletal and cardiovascular risks.

# Monitoring Roles

[name] (Lead PI) and [name] (PI) will oversee data collection monitoring and all issues related to participant safety data collection protocols, and participant confidentiality. [name] will oversee the training of lab team members and monitor training sessions. Lab team members who become aware of any adverse event or unanticipated problems related to the study will notify [name] immediately.

[name], a physician who specializes in cardiovascular disease will advise on cardiovascular safety and approve participation of each participant. [name] (rheumatologist, epidemiologist), an expert in knee OA management, will advise on clinical and safety considerations relevant to OA.

The Institutional Review Board (IRB) is a committee established by the grantee/sponsoring institution to review and approve research involving human subjects. The IRB ensures human subject research is conducted in accordance with all federal, institutional, and ethical guidelines.

Based on previous experience with HIIT and knee OA patients, it is not anticipated that there will be any serious physical or psychological adverse events associated with this study. However, federal regulations require prompt reporting to the University of North Carolina at Chapel Hill Institutional Review Board (IRB), all injuries, adverse events, or other unanticipated problems involving risks to patients or others that occur in the course of a patient's participation in this research study.

# **Routine Safety Reports**

All adverse events and study-related safety events will be collected by Drs. [name] and [name] and coinvestigators ([name], [name], [name]) and will be reported to the Thurston Arthritis Research Center Methodology Core, which works directly with the Regulatory Core of the NC TraCS Institute for monitoring adverse events of research. The PI's will review aggregated unanticipated problems and adverse events on a monthly basis, or more often if urgent matters arise. This summary will be reported to the IRB as necessary.

# **Expedited Reports - Serious Adverse Events**

We do not expect any serious adverse events to occur based on our previous experience with HIIT and knee OA patients. However, in the event that two adverse events are classified as either moderate or severe, the study will be placed on hold in order to reassess the study procedures in order to decrease the risk of another adverse event.

All interventional studies, independent of phase or type, must report Serious Adverse Events (SAEs). All SAEs, unless otherwise specified in the protocol and approved by the IRB and the National Institute of Child Health and Human Development (NICHD), require expedited reporting by the Principal Investigators (Drs. [name] and [name]). If a potential SAE is reported to any study personnel, the study personnel should make [name] aware of the potential SAE at once. [name] will personally collect information from healthcare professionals involved in the study, the study participant and close relatives (if possible), and other study personnel.

Drs. [name] and [name] will provide written documentation to 1) the Institutional Review Board at the University of North Carolina at Chapel Hill and 2) the Thurston Arthritis Research Center Methodology Core (serving as a data safety monitoring board), within 48 hours of learning about the SAE. A single form (Appendix F) will be completed and sent to both the Safety Officer and the IRB by electronic mail with signatures of the Principal Investigator, Drs. [name] and [name]. The action regarding the treatment of that specific patient taken by [name] and/or lab members will be indicated on the form, as well as actions that are taken for the study in general (No action, modification of HIIT, modification of consent documents to include a description of newly recognized risks, revised protocol to eliminate apparent immediate hazards to subjects, other). The Thurston Arthritis Research Center Methodology Core and IRB will be asked to notify Drs. [name] and [name] if they disagree with the specific actions taken within 72 hours. The immediate reports should be followed by detailed, written reports as soon as possible. Follow up information may be required.

